8. REGULATORY ISSUES

Topical Nasal Challenge Agents

All our challenge agents are used to elicit an inflammatory response, and not employed for therapeutic benefit.

Hence these agents are regarded by the UK regulatory authority (the Medicines and Healthcare Regulatory Authority, MHRA) as Non-Investigative Medicinal Products (non-IMP) (92).

For this reason, the challenge agents do not have to be manufactured according to Good Manufacturing Practice (GMP).

A proposal to employ these nasal challenges does not require supervision by the MHRA, where we have contacted the Clinical Trials Dept and [name].

Vitamin D3

We have obtained confirmation from the MHRA and the manufacturers of Vitamin D3 (Lamberts Healthcare Ltd) that the vitamin D3 is classified as a food supplement and not an Investigative Medicinal Product (IMP).

8.1 ETHICS APPROVAL

The Chief Investigator has obtained approval from the Research Ethics Committee. The study must be submitted for Site Specific Assessment (SSA) at each participating NHS Trust. The Chief Investigator will require a copy of the Trust R&D approval letter before

accepting participants into the study. The study will be conducted in accordance with the recommendations for physicians involved in research on human subjects adopted by the 18th World Medical Assembly, Helsinki 1964 and later revisions.

Only for subjects receiving tuberculin we shall propose a limited range of genetic tests. This is because the immune response to TB is strongly influenced by a limited number of genes (61,93). These samples will be handled strictly under the Human Tissue Act, and data handled in a confidential manner, with no reporting back to the subject.

8.2 CONSENT

- Anonymised samples will be aliquoted and stored prior to analysis in all cases.
- An option for the participant to provide blood samples for DNA analysis has been included for Part B
- An option for the participant to take part in a reproducibility element has been included for Part B
- All DNA blood samples will be stored as per Human Tissue Act regulations.
- All publications will be anonymised.

Consent to enter the study must be sought from each participant only after a full explanation has been given, an information leaflet offered and time allowed for consideration. Signed participant consent should be obtained. If potential volunteers are identified from sites other than Imperial College Healthcare NHS trust, they will be asked to sign a pre-screening consent form that seeks permission for their identifiable demographic and medical data to be transferred from their base hospital to Imperial College Healthcare NHS trust. This data will be transferred on a password protected spread sheet via secure NHS mail and will subsequently be stored on a secure trust network that is restricted to researchers from the Imperial Clinical Respiratory Research Unit (ICRRU) based at St Mary's Hospital, Paddington, London. The right of the participant to refuse to participate without giving reasons must be respected. After the participant has entered the study the clinician remains free to give alternative treatment to that specified in the protocol at any stage if he/she feels it is in the participant's best interest, but the reasons for doing so should be recorded. In these cases the participants remain within the study for the purposes of follow-up and data analysis. All participants are free to withdraw at any time from the protocol treatment without giving reasons and without prejudicing further treatment.

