APPENDIX 2C

Appendix 2C

Nasal Challenge with Resiquimod (TLR7/8)

Part B. 0.02µg/kg to 0.05µg/kg with Blood Sampling and Nasal Curettage

Single Cohort of up to 46 Volunteers

(12 non-atopic; 12 atopic, 16 allergic asthma, 6 non-allergic asthma)

Each subject given saline control and between resiquimod 0.02 µg/kg to 0.05µg/kg per nostril
4 subjects with asthma initially given half the dose of healthy volunteers

Safety Observations

Nasal mucosal exam, nasal & systemic symptoms and spirometry checked hourly until 10h and at 24h

Screening

- Skin AG pricks
- ECG
- Blood DNA
- Nasal curettage
- Bloods
- Nasal/pharyngeal swab

d-7

Nasal Challenge Saline

d0

Nasal Challenge Resiquimod 0.02 µg/kg to 0.05 µg/kg

d7

Repeat Nasal Challenge (up to 6 from each group) 0.02 µg/kg to 0.05 µg/kg

>6 weeks

Nasal Challenge Procedures

- Initial bilateral lavage at -20m
- PNIF and nasal symptoms: -30m, 15m, 30m, 45m, 1-24h
- Nasal SAM: -30m, -10m, 15m, 30m, 45m, 1-24h
- Nasal curettage: d-7, 8h and 24h (up to 4/timepoint)
- Blood up to 20ml x4: -20m, 4h, 8h & 24h

Nasal SAM, neat:

- Mass Spectrometry
- Lipidomics
- Prostanoids

Nasal SAM, eluate:

- Cytokines & chemokines

Nasal curettage:

- Flow cytometry & transcriptomics

Blood

- Flow cytometry

P
V

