2. STUDY OBJECTIVES

2.1 PRIMARY AND SECONDARY OBJECTIVES

- To develop a set of well-tolerated, robust and reproducible (validated) nasal challenge systems with microbial constituents and allergen. To identify biomarker signatures following different challenges.

- To document a dose response and time course to nasal challenge in terms of cytokine and chemokine release, and nasal epithelial curettage (Rhinoprobe) mRNA expression, cell influx by flow cytometry.
- To provide a set of nasal challenge methods to enable a “proof of target pharmacology” for a novel therapy or vaccine. This may also permit dosage optimisation in relation to clinical efficacy studies.
- To develop real time sampling utilising a special probe that touches the surface of the nasal lining and is linked to a mass spectrometer.

To assess nasal cytokines/chemokines in the nasal mucosa and assess levels of circadian-associated gene expression (BMAL-CLOCK genes) in curettage samples after NAC before and after Vitamin D supplementation.

3. STUDY DESIGN (See Figures above)

Group 1: Nasal challenge with TLR Agonists: This part of the study has a total of 96 subjects divided into two parts; Part A and B.

Part A: We shall have 3 cohorts of 8 healthy volunteers (4 of the 8 having atopy). There will be a separate cohort of 8 subjects for each challenge agent (MPLA, poly-ICLC, and resiquimod).

A careful incremental ascending dose tolerability study will be performed: starting with saline and then giving single doses of 10, 100, 500µg and up to 1000µg of a given challenge agent in volumes ranging from 100µl to 500µl per nostril.

Part A, N= 24

- | | |
|---------------|-------|
| a. MPLA | n = 8 |
| b. Poly-ICLC | n = 8 |
| c. Resiquimod | n = 8 |

For each challenge agent we shall initially take serial SAM samples over 8 hours, and assess the cytokine and chemokine response.

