Part B: When we have defined the top safe dose, we shall study up to a further 16 subjects for each challenge agent (up to 46 for resiquimod): and include extra sampling for nasal curettage and blood flow cytometry. For those volunteers in the resiquimod arm of the study, we will invite some of the participants (up to 6 in each group) for a repeat challenge at least 6 weeks after the prior challenge. In January 2016 we updated the protocol to move to a weight based dosing regimen for administering resiquimod. We intend to challenge 6 volunteers (mix of healthy volunteers and those with allergic rhinitis) at a dose of 0.02µg/kg per nostril, which equates to 1µg/100µl per nostril in a 50kg volunteer. For the asthma group, we intend to challenge 4 people at half the dose given to the healthy group. The maximum tolerated dose will then be used for the remaining subjects in the study, [We will not use resiquimod at a dose higher than 10µg/100µl per nostril for the remainder of the study.](#)

Part B, N = 90

- | | |
|---------------|--|
| a. MPLA | n = 16 |
| b. Poly-IC | n = 16 |
| c. Poly-ICLC | n = 16 |
| d. Resiquimod | n = 46 (12 healthy, 12 atopic, 16 allergic asthmatic, 6 non-allergic asthma) |

Group 2: Nasal challenge with tuberculin: This part of the study has a total of 32 subjects divided into two parts; Part A and B.

Part A: This involves 4 cohorts of subjects with defined latent TB.

A careful incremental ascending dose tolerability study will be performed: starting with single doses of:

Part A, N=16

- A. Subjects with Latent TB
 - a. 0.1 TU/100µl/nostril, n = 4
 - b. 1.0 TU /100µl/nostril, n = 4
 - c. 2.0 TU /100µl/nostril, n = 4
 - d. 5.0 TU /100µl/nostril, n = 4

For each agent we shall look at tolerability and initially take serial SAM samples over the next 7 days to assess the cytokine and chemokine response.

Part B: When we have defined the top safe dose, we shall study up to a further 16 subjects with the top tuberculin dose: and include extra sampling for nasal real time mass spectrometry, nasal curettage and blood flow cytometry.

Part B, N=16

- A. Subjects with Latent TB,
 - a. 10.0 TU /100µl/nostril, n = 8
- B. Healthy volunteers,
 - b. 10.0 TU /100µl/nostril, n = 8

Group 3: Nasal challenge with allergen (Timothy grass pollen): This part of the study has a total of 70 subjects divided into two parts; Part A and B.

Part A Nasal challenge with allergen and vitamin D3 supplementation or placebo:

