This involves a total of 24 subjects who are allergic to grass pollen and are vitamin D insufficient. Participants are divided into 2 groups (vitamin D supplementation and placebo arms). This is a randomized, double-blind, placebo-controlled study. They will have two NAC; one before and one after supplementation. At each NAC visit, subjects will be given a single dose of Timothy grass pollen (*Phleum P5*) allergen:

The *Phleum P5* is given as 5000 SQ-U = 1µg/100µl per nostril.

After being randomized into one of the two groups they will receive their first NAC and subsequently take vitamin D3, 4000IU (n=18) or placebo (n=6) orally once daily at approximately the same time each morning until their second NAC. This second NAC will take place between 28-35 days. During both days of NAC, serial SAM samples will be taken and nasal curettage performed. Blood samples will also be taken for routine safety tests, peripheral blood mononuclear cells (PBMC) *in vitro* assays, vitamin D, calcium, cortisol, melatonin and whole blood transcriptomics (circadian-associated genes).

Part A, N=24

- A. Subjects with grass pollen allergy and insufficient Vitamin D3
 - a. Subjects taking Vitamin D3 supplementation n = 18
 - b. Subjects on placebo n = 6

Part B: Nasal challenge with allergen involves a total of 46 subjects:

This is divided into 4 groups of subjects given a single dose of Timothy grass pollen (*Phleum P5*) allergen:

The *Phleum P5* is given as 5000 SQ-U = 1µg/100µl/nostril

Subjects with hay fever out of season (n=12)

Subjects with allergic asthma out of season (n=12): half taking no anti-inflammatory drugs, half receiving combined inhaled corticosteroids and long-acting beta-agonists (ICS/LABA)

Non-atopic healthy controls (n=6)

Subjects with hay fever out of season who will trial a novel nasal special sampling probe (SSP) for real time mass spectrometry (n=16)

N= 46

- a. People with hay fever, n = 12
- b. People with allergic asthma, n = 12
- c. Healthy, non-atopic people, n = 6
- d. People with hay fever, n = 16

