Then the second subject will be observed over **≥48h**, again only proceeding if there are no adverse events in the first 2 subjects

Then the 3rd and 4th subjects can be given nasal challenge simultaneously.

There will be follow-up for all subjects given nasal challenge at 7d after challenge.

Ascending Dose Protocol in Subjects with Latent TB (LTB)

Single dose of tuberculin PPD per subject (spray each nostril),
4 subjects per dose without placebo initially, 4 groups of 4:

- 0.1TU/nostril, from tuberculin 20U/ml, n=4
clinical observations: nasal examination and systemic features (BP, pulse, temperature) every 30min for 2h
- 1.0TU/nostril, from tuberculin 20U/ml, n=4
clinical observations, nasal examination and systemic features (BP, pulse, temperature)
- 2.0TU/nostril, from tuberculin 20U/ml, n=4
clinical observations, nasal examination and systemic features (BP, pulse, temperature)
- 5.0TU/nostril, from tuberculin 100U/ml, n=4
clinical observations nasal examination and systemic features (BP, pulse, temperature)

After 5.0TU has been administered clinical data and MSD analyses of nasosorption eluates from all doses will be made.

Then the decision will be made on whether to continue 5.0TU nostril or move up to 10.0TU/nostril, from tuberculin 100U/ml

Highest dose nasal tuberculin cohort

1. Decision on top dose.
N=8 on top dose with latent TB, 6 versus 2 placebo
N=8 healthy IGRA test negative, 6 versus 2 placebo
2. Nasosorption:
 - cytokines and chemokines: - elute with buffer
 - lipidomics, prostanoids, resolvins, metabolomics – spin off neat
3. Nasal scrapes for:
 - flow cytometry on T cells and DCs
 - transcriptomics

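### The lead objective claims reproducible, validated challenge systems for all agents, but only two of six agents have a described repeat challenge and no repeatability estimate is planned for any

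*Combined protocol and SAP*

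**What the plan says.** Section 2.1 puts this first among the objectives: "To develop a set of well-tolerated, robust and reproducible (validated) nasal challenge systems with microbial constituents and allergen". It does not limit the aim to particular agents.

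The repeat challenges described are these:

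- **Resiquimod.** Section 3, Group 1 Part B: "we will invite some of the participants (up to 6 in each group) for a repeat challenge at least 6 weeks after the prior challenge". The Appendix 2C diagram shows the same step, "Repeat Nasal Challenge (up to 6 from each group"), and lists the groups as "12 non-atopic; 12 atopic, 16 allergic asthma, 6 non-allergic asthma". It gives the dose of the first and of the repeat challenge as the same range, 0.02 to 0.05 µg/kg.
- **Allergen, ViDAR.** Section 3, Group 3 Part A, on the 24 subjects (18 vitamin D, 6 placebo): "They will have two NAC; one before and one after supplementation". The allergen dose is fixed and the second challenge follows at 28 to 35 days. Section 2.1 uses these pairs for the comparison before and after vitamin D.

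For tuberculin, Section 6 specifies "Single dose of tuberculin PPD per subject". For MPLA, poly-IC and poly-ICLC, Section 3 describes up to 16 further subjects each in Part B and mentions no second challenge.

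Section 8.2 states that "An option for the participant to take part in a reproducibility element has been included for Part B", without naming an arm.

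Section 7 plans plots, summary statistics, Wilcoxon and Mann-Whitney comparisons with placebo, differences from baseline, and areas under the curve.

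**The concern.** Reproducibility of a challenge in a person can be assessed only if that person receives the same challenge at least twice. An agent without such pairs cannot have the property shown, however well the trial runs, and no later analysis can repair that. The objective therefore reaches further than the design.

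The gap has practical weight because the protocol wants these models for showing target pharmacology and for testing new drugs. Planning a paired study of that kind needs the within-subject SD. For allergen and resiquimod the paired data are to be collected, but the plan does not say that this SD will be estimated. A signed-rank test between two occasions would not fill the gap, because a non-significant difference is not evidence of agreement.

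**Working it through.** The plan states no sample size, precision or acceptance criterion for reproducibility, so there is no figure of its own to reproduce first.

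**Step 1. Count the agents with a described same-agent repeat.**

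| Agent | Where described | Possible repeat pairs |
|---|---|---|
| MPLA | Sections 3 and 6; Appendices 2a, 2b | 0 |
| Poly-IC | Sections 3 and 6; Appendix 2b | 0 |
| Poly-ICLC | Sections 3 and 6; Appendices 2a, 2b | 0 |
| Tuberculin | Sections 3 and 6; Appendices 3a, 3b | 0 |
| Resiquimod | Section 3; Appendix 2C | at most 4 groups × 6 = 24 |
| Grass pollen | Section 3, Group 3 Part A | 18 + 6 = 24, of which 6 on placebo |

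The resiquimod groups add up as stated: 12 + 12 + 16 + 6 = 46. TLR Part A gives each subject several challenges, but at ascending doses, so these are not replicates. The five applications over one hour in Appendix 2b form one session. Six agents minus two leaves four without a repeat.

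**Step 2. Check Section 7 for a repeatability analysis.** It names no intraclass correlation (ICC), within-subject SD or coefficient of variation, limits of agreement or acceptance criterion. This holds for resiquimod as for the rest.

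**Step 3. Work out the precision the pairs could give.** Let d be the log-scale change between a subject's two challenges. The within-subject SD is SD(d)/√2. Its 95% interval is the estimate multiplied by √(df/χ²(0.975, df)) and √(df/χ²(0.025, df)), assuming roughly normal log changes.

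- ViDAR placebo arm: df = 6 − 1 = 5. √(5/12.83) = 0.62 and √(5/0.831) = 2.45.
- ViDAR pooled within arms: df = 24 − 2 = 22. √(22/36.78) = 0.77 and √(22/10.98) = 1.42.
- Resiquimod pooled within groups, full uptake and the same dose twice: df = 24 − 4 = 20. √(20/34.17) = 0.77 and √(20/9.59) = 1.44.

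**Step 4. State what the pooled ViDAR figure assumes.** In the placebo arm, Var(d) = 2σ², where σ is the within-subject SD. In the vitamin D arm, if the effect varies between subjects with variance τ², independently of measurement error, Var(d) = 2σ² + τ². Removing the arm means takes out a constant vitamin D shift but not τ². The pooled estimate is therefore repeatability only if τ² = 0; otherwise it overstates σ.

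**Step 5. Compare with an ICC.** The documents give none, so a range of observed values is assumed. With 6 pairs, the one-way 95% interval is −0.33 to 0.91 at 0.5, −0.03 to 0.95 at 0.7, 0.20 to 0.97 at 0.8 and 0.52 to 0.99 at 0.9. A placebo-arm ICC would say little, which favours the within-subject SD.

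**The case against.** The best defence is that Section 2.1 lists exploratory development aims with no success rule, so nothing in the plan formally declares a challenge validated. Reading reproducibility as test-retest agreement in the same person is also an interpretation. That lowers the stakes but does not remove the point: the word validated is in the objective, and Section 8.2 itself speaks of a reproducibility element, which Section 3 realises as a repeat challenge in the same volunteers.

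Several stronger readings are tempting, and the documents do not support them:

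- A reader might infer that only resiquimod can support the claim. Resiquimod and allergen are in the same position: each has pairs and neither has a planned repeatability analysis.
- A reader might say that the ViDAR pairs go unused. They serve the vitamin D comparison and lack only a stated repeatability use.
- A reader might take the resiquimod repeats as identical challenges. They are by invitation, the dose is a range, and no sentence says that a volunteer receives the same dose again.
- A reader might conclude from Section 8.2 that volunteers in other arms are offered a repeat that does not exist. The consent pages are not available, and the line may refer to the resiquimod arm alone, since Section 3 says "For those volunteers in the resiquimod arm of the study, we will invite some of the participants" for a repeat.
- A reader might treat the single-dose wording as proof that there is no repeat. The Appendix 2B heading also names resiquimod, which has one, and ViDAR subjects receive a single dose at each of two visits.

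Some reference diagrams (Appendices 2B, 3B, 4A and 4B) are missing from the copy reviewed. The absence of repeats therefore rests on the body text and procedure tables, which agree with each other.

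**Conclusion.** The concern holds in a limited form. For four of six agents (MPLA, poly-IC, poly-ICLC and tuberculin) the design as described cannot show the reproducibility that the lead objective claims. For the other two, suitable pairs may exist but Section 7 plans no estimate from them.

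The allergen estimate free of vitamin D rests on 6 subjects and would be imprecise. Using all 24 ViDAR subjects narrows the interval markedly, but only under a constant vitamin D shift. The resiquimod interval is a best case that needs all 24 places filled and the same dose on both occasions. All of these factors assume log-normal changes and complete pairs; missing pairs would widen the intervals. Sections 3 and 8.2 differ on the scope of the reproducibility element and need reconciling.

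**What to change.** 1. **Section 2.1.** Limit the reproducible and validated wording to resiquimod and allergen. State the aim for MPLA, poly-IC, poly-ICLC and tuberculin as tolerability and response.
2. **Section 7.** Add a log-scale within-subject SD with 95% CI from the change between the two ViDAR challenges. Make the placebo arm the unconfounded estimate and report the estimate pooled within arms as supportive, with its constant-shift assumption stated. Apply the same statistic to resiquimod pairs in which both challenges used the same dose, pooled within groups, and report how many pairs qualify.
3. **Section 8.2.** Reconcile the reproducibility option with Section 3, so that both name the same arm or arms.

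The cost is two wording changes and one analysis of data already to be collected, with no extra participants, visits or samples. The downside is a narrower claim and a wide interval for the placebo-only allergen estimate.

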8.3 CONFIDENTIALITY

The Chief Investigator will preserve the confidentiality of participants taking part in the study and is registered under the Data Protection Act.

8.4 INDEMNITY

Imperial College London holds negligent harm and non-negligent harm insurance policies which apply to this study.

The College holds two insurance policies which apply to healthcare research.

1. Public Liability (negligent harm)

The College holds Zurich Municipal Public Liability insurance which provides cover in the event that Imperial College is held legally liable for negligent harm caused to a research subject.

2. Clinical Trial (non-negligent harm)

Cover for non-negligent harm arising from an Imperial project is provided by the College's Zurich Municipal Clinical Trials insurance policy. The policy document defines a "clinical trial" very broadly as: "Any investigation or series of investigations conducted on any person for a medicinal purpose".

Consequently, this policy will be relevant if your study involves direct interventions with a research subject.

The non-negligent harm policy specifically excludes cover for claims arising from children aged under five and pregnant women. It has a number of other important exclusions, including, but not limited to, claims arising directly from HIV/AIDS, Hepatitis, Creutzfeldt-Jakob disease, or the use of products or devices designed by Imperial College.

It is usually possible to have the pregnant women and children aged under five exclusions waived on a study-by-study basis following liaison with the Insurer.

<http://www3.imperial.ac.uk/clinicalresearchgovernanceoffice/projectplanning/clinicalresearchofficeapproval/insurance>

8.5 SPONSOR

Imperial College London will act as the main Sponsor for this study. Delegated responsibilities will be assigned to the NHS Trust taking part in this study.

8.6 FUNDING

Imperial NIHR BRC are funding this study

8.7 AUDITS

The study may be subject to inspection and audit by Imperial College London under their remit as sponsor and other regulatory bodies to ensure adherence to GCP and the NHS Research Governance Framework for Health and Social Care (2nd edition).

